3.2. Objectives

Our goal with this research is to examine the feasibility, satisfaction rates, and efficacy of two interventions, Contingency Management (CM) and Brief Motivational Intervention + Substance Free Activities + Mindfulness-Based Adherence Promotion (BSM), to improve buprenorphine-naloxone adherence during the treatment initiation phase (first 5 physician visits). Once feasibility, satisfaction, and efficacy are acquired, Project 4 (the randomized clinical trial associated with the R33 award phase) will be conducted.

Feasibility in this trial is defined as the ability to recruit, treat, and follow up participants within the target timeline and costs. Recruitment, intervention, and retention actuals (vs. goals) will be evaluated by investigators and the Data Safety Monitoring Board (DSMB) which will be convened every 6 months.

Satisfaction will be measured with a measure developed from previous research.

Efficacy will be evaluated in terms of participant adherence to buprenorphine-naloxone treatment: Showing up to scheduled appointments with their physician at the Center for Addiction Science AND the presence of buprenorphine in the participant's urine screen, conducted as a part of buprenorphine treatment.

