3.3. Design and Outcomes

This project will use a randomized design to compare treatment satisfaction and effectiveness of Contingency Management (CM) and Brief Motivational Intervention + Substance Free Activities Session + Mindfulness-Based Adherence Promotion (BSM) for medication adherence in patients who are initiating buprenorphine-naloxone treatment at our Center for Addiction Science (N=40). The interventions will take place across the first 4 physician visits of buprenorphine-naloxone treatment, starting after treatment intake.

Primary outcomes will include feasibility and satisfaction at the fourth weekly intervention visit, and an efficacy comparison of intervention group differences in buprenorphine-naloxone treatment adherence, defined as (1) attendance at physician visit AND (2) buprenorphine-naloxone presence in urine toxicology.

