3.6.2. Sessions 1-4: Intervention Treatment

- 1) Assessment questionnaires with interventionist
 - a) Assessment questionnaires completed (10 minutes)
- 2) Engage in either CM (2 minutes) or BSM (30 minutes)
 - a) BSM:
 - i) All BSM sessions will be audio-recorded in order for the study staff to evaluate treatment fidelity. Participants will be informed when the recording device is on, and permission to record will be obtained as soon as the recording device is started. Participants may refuse to have the session recorded and still participate. Audio recordings will be de-identified and labeled with a Study ID number stored on an encrypted computer.
 - b) CM:
 - i) A number wheel (pickerwheel.com) with varying levels of gift cards (ranging from \$25 to \$100) will be available.
 - ii) Urine toxicology will be obtained from the chart to assess presence of buprenorphine in urine (criteria for reward).
 - iii) Participants will be informed of the buprenorphine toxicology result.
 - (1) **IMPORTANT: IT IS BUPRENORPHINE IN URINE THAT RESULTS IN A GIFT CARD WIN.**
 - (2) **We ARE NOT providing feedback to the participant about the use of illicit substance presence in urine as this is not criteria for reward.**
- 3) Chart Review Following Intervention

- a) Information about buprenorphine-naloxone dose, all urine screen results (13 panel), and other substance use disorder diagnosis will be copied from the participant's medical chart.
- b) Opioid prescriptions will be obtained from prescription drug monitoring database.

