8.2. Enrollment

8.2.1. Consent

Project staff will answer any questions about the entire process and an informed consent will be obtained. No study assessment will take place prior to obtaining consent from each subject. Standard language in our consent form assures the participants of the confidential nature of the study and the ability to withdraw from the study at any time. The consent forms will contain HIPAA language. This study will be approved by the UTHSC IRB.

Participants will be given a copy of the consent statement for their records. The consent discussion will be documented on the eligibility page of the FileMaker Database.

Participants will be informed that regardless of their adherence to clinic visits or use of buprenorphine-naloxone (the primary study outcome), they will be eligible to complete assessments at scheduled intervals and will be compensated for these assessments. This will enable the study team to discover whether drop out of treatment leads to relapse to opioids and if treatment is sought elsewhere.

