12. MEASURES

12.1. Table 1. List of Measures

Measure	Time to Complete (minutes)	Baseline	1,2, 4, and 8 week sessions	8 week blind	Medical Chart at 30 days
Contact Information	1	X			
Referral source (how did they get to the CAS)?	<1	X			
Screening Questionnaire	<1	X			
Exclusion reason (if applicable)	n/a				
Demographics (gender/race/ethnicity/education/zip code/insurance)	3	X			
Opioid Use Disorder (Diagnostic and Statistical Manual of Mental Disorders-5) ⁹³ interview	1	X			
Attended first physician visit	n/a		X		
Attended second physician visit	n/a		X		
Attended third physician visit	n/a		X		
Attended fourth physician visit	n/a		X		
Number of treatment visits attended (allow for drop out, drop back in): CUMULATIVE ADHERENCE	n/a				X
Urine Toxicology (buprenorphine and all other substances)	n/a	X	X		X
Timeline followback on alcohol, substance use, and opioid use	3	X	X		
Delay Discounting ⁵⁸	2	X		X	
Opioid Purchase Task ⁴⁶	1	X	X		
Engagement in Substance Free Activities ⁵⁴	2	X		X	
Time Spent On Activities	2	X			
Opioid Craving Symptoms ⁹⁵ (Opioid Cravings Scale)	1	X	X		
Buprenorphine-Naloxone dose log (did you miss any days?)	<1		X		
Dosage of Buprenorphine-Naloxone Prescribed (obtained from medical record at each session)	n/a	X	X		X
Treatment Satisfaction	4			X	
Prescription Drug Monitoring data	n/a	X	X		X
PEG for Chronic pain (3 items)	<1	X	X		
EQ5D5L (6 items) Quality of life for cost-effectiveness analyses	3	X		X	
PHQ-2 depression 2 items	<1	X	X		
GAD 2 anxiety 2 items only (also a 7 item version)	<1	X	X		
Treatment history (times in treatment, medication used)	<1	X			
Economy Contribution (3 items)	<1	X	X		
If dropped out: Are you receiving but (or opioid replacement) treatment somewhere else?	<1		X		
Adverse Events	<1		X		
Participant time to complete all measures at sessions:		20.5	11	10	n/a

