12.2.7. Adherent for first follow up physician visit

Showed up for Center for Addiction Science appointment at scheduled day/time?	Yes / No
AND	
Had buprenorphine in urine screen (either at the visit or when urine specimen came back from lab)?	Yes / No
If both items answered “Yes” then adherent is affirmed through Filemaker calculation	

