Statistical Analysis Plan: SMART Project 3 (Efficacy Study)

Because these analyses will focus on determining and intervention feasibility and satisfaction, and preliminary intervention effect sizes (with less concern focused on testing for statistical significance), outcome analyses will be conducted using a separate analysis for each outcome at each follow up observation. To compare groups, baseline and follow up variables will be entered into a 5 (baseline vs. follow ups at 1, 2, 3, and 4 weeks) by 2 (CM vs. BSM) analysis of variance (ANOVA) which will yield effect sizes for time, and interactions of time by intervention. The primary dependent variables will be attendance at physician visits, saliva drug screen data (positive for buprenorphine and negative for illicit opioids), and prescription drug monitoring. We hypothesize that a greater number of CM participants will demonstrate adherence to buprenorphine-naloxone than BSM, but that those randomized to BSM will report increased time allocated to substance-free activities, decreased delayed reward discounting, and demand for opioid.

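### The SAP's primary variables omit the protocol's adherence endpoint (attended and buprenorphine in urine) and name a saliva screen for which the supplied protocol text describes no collection

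*SAP*

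**What the plan says.** The SAP is a single paragraph. On the primary variables it reads: "The primary dependent variables will be attendance at physician visits, saliva drug screen data (positive for buprenorphine and negative for illicit opioids". Prescription drug monitoring completes the list. Each outcome is to be analysed on its own at each follow-up. The first hypothesis is that "a greater number of CM participants will demonstrate adherence to buprenorphine-naloxone than BSM". This is the SAP's only mention of adherence, and it carries no definition.

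The protocol does define it. Section 3.2 puts efficacy as "Showing up to scheduled appointments with their physician at the Center for Addiction Science AND the presence of buprenorphine", the specimen being the urine screen done as part of treatment. Section 3.3 places the group comparison of adherence among the primary outcomes, with adherence "defined as (1) attendance at physician visit AND (2) buprenorphine-naloxone presence in urine toxicology". Sections 12.2.7 to 12.2.10 (the third is numbered 11.2.9) implement this. One form per follow-up visit asks about attendance and about buprenorphine in the urine screen, and if both answers are Yes, "then adherent is affirmed through Filemaker calculation".

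On the specimen, section 3.6.2 says: "Urine toxicology will be obtained from the chart to assess presence of buprenorphine in urine". Table 1 in section 12.1 has the row "Urine Toxicology (buprenorphine and all other substances" and no row for saliva. The toxicology form (numbered 11.2.12) and the final chart review (3.6.4) also refer to urine.

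**The concern.** The quantity that the protocol calls efficacy is not among those the SAP says it will analyse. The nearest SAP variable, the drug screen, differs from the protocol's in specimen and in content: it must also be negative for illicit opioids. The protocol's adherence definition has no such condition, and section 3.6.2 says illicit-substance results do not count towards the contingency management (CM) reward.

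The SAP's purpose includes preliminary effect sizes, beside feasibility and satisfaction, and section 3.2 makes Project 4 follow once feasibility, satisfaction and efficacy have been obtained. If the SAP is followed literally, no effect size is produced for the endpoint the protocol defines, and one listed variable has no described source of data. The hypothesis about adherence is then not tied to any listed variable.

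**Working it through.** The documents give no figure to reproduce. Section 3.5 sets 20 per arm, without rates, power or a target difference. The check is a comparison of texts, followed by an illustration of size.

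**Step 1. The two documents side by side**

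| Feature | Protocol (3.2, 3.3, 12.2.7 to 12.2.10) | SAP |
|---|---|---|
| Attendance | First condition of the composite | Separate primary variable |
| Buprenorphine | Second condition of the same composite | Part of a separate screen variable |
| Illicit-opioid result | Not part of adherence | Must be negative |
| Specimen | Urine | Saliva |
| Missed visit | Non-adherent, because the first item is No | Not stated |
| Prescription monitoring | Collected (Table 1), not among the primary outcomes in 3.3 | Primary |
| Adherence | Defined, and derived at each visit | Hypothesis only, undefined |

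**Step 2. What separates the SAP screen from the composite.** A clinic urine result presupposes a visit. A urine screen with no opioid-negative condition, and with a missed visit scored as a failure, would therefore nearly reproduce the composite. The SAP departs on two of these three features (specimen and opioid-negative condition) and is silent on the third.

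**Step 3. Illustrative size at one visit.** All rates here are assumptions. Let *a* be attendance, *p* the share of attenders positive for buprenorphine, and *s* = 0.75 the share of positives who are also opioid-negative, equal in both arms.

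- Composite: *a* × *p*
- SAP screen, missed visit as failure: *a* × *p* × *s*
- SAP screen, missed visit dropped: *p* × *s*

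Differences between CM and the comparison arm (BSM), in percentage points:

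| Attendance CM / BSM | Positive CM / BSM | Composite | SAP screen, missed = failure | SAP screen, missed dropped |
|---|---|---|---|---|
| 70% / 60% | 90% / 90% | 63 − 54 = +9 | 0.75 × 9 = +6.75 | 0 |
| 80% / 60% | 90% / 90% | 72 − 54 = +18 | 0.75 × 18 = +13.5 | 0 |
| 90% / 60% | 90% / 90% | 81 − 54 = +27 | 0.75 × 27 = +20.25 | 0 |
| 80% / 60% | 95% / 85% | 76 − 51 = +25 | 0.75 × 25 = +18.75 | 0.75 × 10 = +7.5 |

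**Step 4. Precision.** The 95% half-width for the composite difference at 72% against 54% is 1.96 × √(0.72 × 0.28/20 + 0.54 × 0.46/20) = 0.294, about 29 points. The same formula gives 30.4 points at 63% against 54%, 27.8 at 81% against 54%, and 28.8 at 76% against 51%. The largest shift between definitions in the table is 27 − 0 = 27 points, in the third row, where the half-width is 27.8. No shift exceeds the half-width for its row.

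**The case against.** The best defence is that the two documents should be read together. The protocol defines adherence, the database computes it at every follow-up visit, and an analyst testing the SAP's hypothesis could simply use that variable. On this view the SAP merely lacks a cross-reference. Part of this stands: the definition exists, which is why the remedy is short. But the SAP does more than stay silent. It gives an explicit primary list that leaves the composite out, and its screen variable has a different specimen and an added condition.

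Three further points are fair.

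- Section 3.3 words its primary outcomes as an open list, so additional primary variables in the SAP are not in themselves a contradiction. The defect is the omission.
- The protocol's usage is not uniform. Section 8.5.1 calls a participant adherent on urine alone when deciding the wheel spin, and Table 1 and section 12.2.11 label a count of attended visits as cumulative adherence. These looser labels leave the efficacy definition in 3.2 and 3.3 intact, but they make an explicit SAP definition more useful.
- This is a 40-person pilot in which the SAP plays down significance testing. That removes any argument about lost significance. It does not settle which effect size is to be reported.

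A reader might also take section 8.2.1 as proof that the composite is the primary outcome. It does not show that. The phrase is "adherence to clinic visits or use of buprenorphine-naloxone (the primary study outcome": it says or, and the parenthesis may attach only to the second item.

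**Conclusion.** The point holds. The SAP omits the protocol's efficacy endpoint from its primary variables and names a specimen for which the supplied protocol text describes no collection. The conclusion rests on the wording alone; the rates above only illustrate size. Under them, composite differences of 9 to 27 points correspond to about 7 to 20 on the SAP screen with missed visits as failures. With 20 per arm such shifts lie within sampling error. The harm is that the wrong quantity may be reported.

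Three stronger readings are tempting and are not supported:

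- *The SAP would hide a CM benefit.* The zeros in the last column follow from assuming equal positivity in both arms and from dropping missed visits, which the SAP does not specify. Attendance is analysed in any case, so an attendance benefit would show there.
- *Saliva is certainly not collected.* Some protocol passages were not available. The statement covers the supplied text, which includes the schedule of measures and the forms.
- *The 30-day chart review must also use the composite.* Sections 3.4.4 and 3.6.4 list attendance and urine results as data to collect, without a rule combining them.

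**What to change.** In the SAP:

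1. Replace saliva with urine.
2. Name the composite of section 3.3, as derived in 12.2.7 to 12.2.10, as the primary efficacy (adherence) variable at each of the four follow-up visits. State that a missed visit is non-adherent, as the two-item form already implies. Report the CM minus BSM difference at each visit with a 95% interval; this fits the SAP's existing provision for visit-by-visit analyses.
3. Keep attendance, buprenorphine-positive and opioid-negative urine, and prescription monitoring as separately labelled outcomes, distinct from adherence.

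The cost is a few sentences. The composite is already calculated, and no participants, visits or specimens are added.

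Optional clarifications, not needed for the fix:

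- how to score an attended visit with no screen result (one participant is 1/20 = 5 points of an arm), and whether the form should offer a no-result option;
- whether the 30-day review uses the same composite;
- whether a visit rescheduled within the window (8.5.1, 8.10) meets the form's condition of attending at the appointed time;
- whether buprenorphine counts in the prescription field (12.2.22);
- that cumulative adherence (12.2.11) counts attendance only.

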3.5.2. Inclusion/Exclusion

Participants must be 18 years of age or older and presenting for buprenorphine-naloxone treatment. Patients must be eligible to receive buprenorphine-naloxone medication (e.g., Suboxone, Bunavail, Zubsolv) during their visit at CAS. This study is open to all eligible participants.

Notably, due to the nature of medical treatment, approximately 5% of new patients will not follow the "regular" intake course of buprenorphine due to previous treatment and/or treatment initiation using injectable depot buprenorphine administration (which requires fewer physician visits). Because all patients initiating treatment are at risk for drop out/low adherence, we wish to enroll these participants if at all possible under the stringent timelines for this study. We will therefore enroll unusual buprenorphine-

naloxone initiation timelines on a case by case basis, dependent upon the ability to complete study procedures within the study timeline.

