12.2.3. Screening Questionnaire

	Inclusion	
1.	Presenting for their intake visit to the Center for Addiction Science for treatment of opioid use disorder	Yes / No If no: Exclude

2.	Access to a telephone	Yes / No If no: Exclude
3.	Eligible for receipt of buprenorphine-naloxone medication (e.g., Suboxone, Bunavail, Zubsolv)	Yes / No If no: Exclude
4.	Able to understand consent procedures	Yes / No If no: Exclude
Exclusion		
5.	Have a known contraindication to buprenorphine-naloxone medication treatment for opioid use disorder	Yes / No If yes: Exclude

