12.2.10. Adherent for fourth physician visit

Showed up for Center for Addiction Science appointment at scheduled day/time?	Yes / No
AND	
Had buprenorphine in urine screen (either at the visit or when urine specimen came back from lab)?	Yes / No
If both items answered "Yes" then adherent is affirmed through Filemaker calculation	

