12.2.22. Prescription Drug Monitoring data

Number of opioid prescriptions found in the prescription drug monitoring database since last visit	#
--	---

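### The SAP puts yes/no and count outcomes into a 5 × 2 ANOVA with a baseline at which attendance is constant; a common error variance would usually overstate late-visit precision for attendance

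*SAP*

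**What the plan says.** The SAP is one paragraph. It names as primary dependent variables "attendance at physician visits, saliva drug screen data (positive for buprenorphine and negative for illicit opioids), and prescription drug monitoring", and enters baseline and follow-up values into a "5 (baseline vs. follow ups at 1, 2, 3, and 4 weeks) by 2 (CM vs. BSM) analysis of variance (ANOVA") to obtain effect sizes for time and for time by intervention. The sentence before says that "outcome analyses will be conducted using a separate analysis for each outcome at each follow up observation". It gives effect sizes priority over significance tests. It names no error term, sphericity correction, interval method, significance level, or model for binary or count data.

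The Protocol fixes the scale of each variable:

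- **Attendance and screen.** Sections 12.2.7 to 12.2.10 record two yes/no items at each of four return visits: "Showed up for Center for Addiction Science appointment at scheduled day/time", and buprenorphine found in urine. (The SAP says saliva; that mismatch does not affect this point.)
- **Prescription monitoring.** Section 12.2.22 records "Number of opioid prescriptions found in the prescription drug monitoring database since last visit".
- **Baseline.** The screening questionnaire (12.2.3) excludes anyone not "Presenting for their intake visit to the Center for Addiction Science for treatment of opioid use disorder". Table 1 (12.1) lists attendance for the four return visits only, but schedules "Urine Toxicology (buprenorphine and all other substances") and prescription monitoring at baseline as well.

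**The concern.** ANOVA assumes one error variance across its cells. A yes/no outcome with probability p has variance p(1 − p), which changes as p changes over visits. For attendance the first of the five levels is degenerate: p = 1, variance 0, and no possible arm difference. Averaging that zero into a common error variance lowers it, and the visits where attendance has fallen furthest towards one half are then given too small a standard error. Any effect size scaled by that error variance is affected in the same way.

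This matters because the pilot exists to supply preliminary effect sizes, and Protocol 3.2 makes Project 4 follow from its results. An interval that is too narrow at the last visits would give the planners of Project 4 false confidence in the arm difference. The conflict between the two sentences adds to this: as written, two analysts could produce different standard errors from the same plan.

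**Working it through.** The plan gives no rate, standard deviation, effect size or power to reproduce.

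**Inputs.** 20 per arm (Protocol 3.5); four return visits plus baseline; attendance = 1 at intake, inferred from 12.2.3. Assumed, because the documents do not state them: attendance by visit, the drop-out pattern, and a two-sided nominal 5% level.

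**Formulas.** At one visit the standard error (SE) of the arm difference is √(2p(1 − p)/20). With a common variance, p(1 − p) is replaced by its mean over the five time points. That mean is the usual pooled variance for an arm contrast at one visit, whether the ANOVA has a single residual or combines between- and within-person strata.

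**Worked case, path 1 / 0.9 / 0.8 / 0.65 / 0.5.** The variances are 0, 0.09, 0.16, 0.2275 and 0.25, with mean 0.7275/5 = 0.1455.

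- Pooled SE = √(2 × 0.1455/20) = 0.121.
- Visit-4 SE = √(2 × 0.25/20) = 0.158; ratio 0.76.
- Half-width at visit 4: 1.96 × 0.121 = 0.24 pooled, against 1.96 × 0.158 = 0.31.
- Visit-1 SE = √(2 × 0.09/20) = 0.095, so there the pooled SE is too large.

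**Range of assumed paths.** Coverage is that of a nominal 95% pooled-variance interval for the visit-4 difference. It was simulated with no arm difference, using 20,000 trials per setting for the first three rows and 6,000 for the rest. In the last five rows the span covers different patterns of within-person correlation.

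| Attendance at intake and visits 1–4 | Mean p(1 − p) | Pooled SE | Visit-4 SE | Ratio | Coverage |
|---|---|---|---|---|---|
| 5% persistent drop-out per visit (ends 0.81) | 0.082 | 0.090 | 0.123 | 0.74 | 84% |
| 10% per visit (ends 0.66) | 0.133 | 0.116 | 0.150 | 0.77 | 86% |
| 15% per visit (ends 0.52) | 0.163 | 0.128 | 0.158 | 0.81 | 88% |
| 1/.95/.92/.90/.88 | 0.063 | 0.080 | 0.103 | 0.77 | 85–88% |
| 1/.9/.85/.8/.75 | 0.113 | 0.106 | 0.137 | 0.78 | 86–88% |
| 1/.9/.8/.65/.5 | 0.146 | 0.121 | 0.158 | 0.76 | 85–86% |
| 1/.7/.6/.5/.4 | 0.188 | 0.137 | 0.155 | 0.89 | 92–93% |
| 1/.6/.4/.3/.2 | 0.170 | 0.130 | 0.126 | 1.03 | 96% |

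With visit 4's own variance, coverage was 94–96% throughout. Protocol 12.2.11 allows for drop-out and return. Letting drop-outs return under the 5–15% rates still left pooled coverage short, within 84–89% overall.

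**Time-by-arm test, same null simulations.**

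- Uncorrected repeated measures: 7.5%, 7.6% and 7.2% rejection for 5%, 10% and 15% persistent drop-out, and 5.2–7.7% over the other paths.
- With Greenhouse–Geisser correction: 3.1–4.9%.
- One residual for all observations: 0.4–3.2% when visits correlate within person, and 6.1–6.8% if they were independent.

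**Two sensitivity checks.**

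- If the baseline level can vary (assumed rate 0.3, then 0.7/0.6/0.5/0.4), the repeated-measures test rejects 4.5–4.7% and pooled coverage is 93–96%.
- Dropping baseline alone does not always cure it: on 0.9/0.8/0.65/0.5, last-visit pooled coverage is still 90–91%.

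**The case against.** The strongest reply is that the SAP never says it pools one error term and plans no intervals. It promises separate analyses per follow-up, which taken literally pool nothing over visits. It also plays down testing, as suits a 40-person pilot, and a difference in means of 0/1 data is still an unbiased difference in proportions. All of this is true. It makes the result conditional on precision being taken from the ANOVA. It does not remove the point, because the only model the SAP names is the 5 × 2 ANOVA, and the two sentences cannot both be followed.

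A reader might go further and infer three things that the documents do not support:

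- **That baseline variance is zero for every primary variable.** This is certain only for attendance. The screen and prescription count are taken at baseline and nothing fixes their values. Protocol 3.5.2 expects about 5% of new patients to follow an unusual course "due to previous treatment and/or treatment initiation using injectable depot buprenorphine administration". No figure here applies to those two variables.
- **That variance peaks at the last visit.** This needs rates that the documents do not give. On the path ending at 0.2 the variance is largest at visits 1 and 2, and the pooled SE is slightly too large at visit 4.
- **That the interaction test is invalid.** It is mildly liberal in one form, close to or below nominal with a standard correction, and conservative with a single residual when visits correlate within person.

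**Conclusion.** The point holds in a limited form. ANOVA is a poor match for yes/no and count outcomes, its baseline level carries no arm information for attendance, and the paragraph contradicts itself on whether visits are analysed jointly or separately.

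If the common error variance is used for attendance, the visit-4 standard error is about 0.74 to 0.81 of its proper size under assumed drop-out of 5–15% per visit, and a nominal 95% interval covers about 84–89% instead of about 95%. The shortfall shrinks on steeper paths and vanishes on the steepest one tried. The interaction test rejects about 5–8% of the time as uncorrected repeated measures, which is a secondary matter.

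The harm is to stated precision, not to the estimated difference itself. Every size given here rests on assumed attendance rates and on the inference that all enrolled participants attended intake.

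**What to change.** Rewrite the SAP sentences as follows.

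1. For the yes/no primary variables, replace the ANOVA with the CM–BSM difference in proportions and a Newcombe (score) 95% interval at each of the four return visits. This delivers the per-visit analysis already promised and removes the contradiction.
2. Do not use baseline attendance as an outcome level.
3. If one summary over visits is wanted, compare the number of adherent visits out of four per participant between arms, or fit a GEE for the risk difference with small-sample-corrected robust standard errors. A logit model with arm-by-visit terms is less safe. At 95% attendance, the chance that at least one arm is 20/20 at visit 1 is 1 − (1 − 0.95^20)² = 1 − (1 − 0.358)² ≈ 59%, and that cell then has no finite estimate.
4. Analyse the prescription count with a method suited to counts; it need not be reduced to any versus none.

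The cost is SAP wording only, with no new data, visits or participants. Late-visit intervals will usually be wider (about 0.31 instead of 0.24 either side in the worked case), and early-visit intervals may be narrower.
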